The primary aim of the study is to determine the effects of beta-glucan, a dietary fiber supplement isolated from baker's yeast, on immune response to the influenza vaccine.

Primary outcome

• Change in immune response to the influenza vaccine after beta-glucan supplementation [Time Frame: 28 days (Baseline (day 1), pre-vaccine visit (~day 1), and study end (~day 28)]; Influenza-specific antibodies (IgM, IgG influenza A and B).

Secondary outcomes

- Inflammatory cytokine profile (TNF-α, IL-1β, IL-6, IL-8, and IFN-γ) [Time Frame: 28 days (Pre-vaccine visit, post-vaccine visit (~day 2-3) and study end)]
- Self-reported incidence of influenza and COVID-19 (Note: Data of subjects reporting incidence of influenza or COVID-19 during the study will be excluded from the final analysis) [Time Frame: 28 days]
- Number of subjects with fever during the study [Time Frame: 28 days] Body temperature (°C)
- Number of subjects with cold and flu symptoms [Time Frame: 28 days] Modified Jackson Criteria
- Fatigue [Time Frame: 28 days (Days 1 28)

Additional information collected

- Demographic data
- Adverse events
- Vaccinations (including COVID-19 booster) received during the month prior to the study start and during the study period
- Compliance

- o Reported intake of the supplement.
- Number of unconsumed supplements (returned)

Study Participants

This is a 2-arm placebo, controlled study. A total of 120 volunteers (60 in each arm) will be recruited for the study. Subjects who do not meet the inclusion criteria or who meet any of the exclusion criteria will not be eligible to participate.

Sample Size Calculation

This is a pilot study, and thus sample size is based on similar published studies.

Inclusion criteria

- 1. Adult volunteers \geq 40 years of age.
- 2. Planning to be vaccinated for influenza
- 3. Have been immunized for COVID-19 (self-disclosure)
- 4. Willing and able to provide written informed consent in English.
- 5. Willing and able to comply with all the study-related procedures, including attending to study visits for blood draw, taking the influenza vaccine, intake of the study supplement, and completing study questionnaires.

Exclusion Criteria

- 1. Demonstrate an inability to comply with the study-related procedures.
- 2. Have a history of a severe reaction or hypersensitivity following vaccination with influenza vaccine, vaccination with any other vaccine containing the same substances, or intake of the study product.
- 3. Be on immune-suppressing treatment (e.g., steroids (last 30 days); cytotoxic drugs, medical surgery, or radiation therapy during the 6 months, previous to enrollment).
- 4. Be concurrently participating in a clinical trial that, in the judgement of the investigator, would interfere with the evaluation of the study outcomes.

Inclusion of Women and Minorities

Both men and women and members of all races and ethnic groups are eligible for this trial.

Recruitment

Potential participants will be recruited through flyers and word of mouth at the University of Florida, Oak Hammock Retirement Community, the Village at Gainesville, and the Gainesville Senior Center. We may also distribute the flyer through the Food Science and Human Nutrition (FSHN) department's website and Facebook page and through FSHN department faculty and staff listservs and Oak Hammock listserv. In addition, we will recruit through flyers and word of mouth at Gainesville and area churches, senior centers, senior communities, and local gyms as well as place an ad in the Gainesville Sun newspaper. Individuals interested in participating will be given the option to attend informational meetings in which the study will be explained in more detail.

Pre-screening will occur via an in-person interview or telephone contact script. The study will be described to the potential study participant using the approved script and the inclusion/exclusion criteria will be read. Potential study participants will be directed to listen to the criteria, without directly answering (stating "yes" or "no") after each criterion is read, and then decide whether they would like to continue with study procedures. If the potential participant is still interested in participating and still believes they may qualify, an appointment will be scheduled for consenting.

Investigational Product (IP)

Manufacturing and Storage

The Investigational Products (beta-glucan and placebo) will be manufactured by Biotec Betaglucans (Lallemand inc., Tromsø, Norway) and provided to the study site, FSHN Clinical Lab, Food Science and Human Nutrition Department. The IP will be carefully stored at the study site in a lockable, limited access area, accessible only by study team personnel in compliance with pertinent regulations. Only authorized persons will have access to the IP. The IP should be stored 3–10 °C.

Beta-Glucan

The product under study is beta-glucan at 500 mg/day (2 capsules per day). The group randomized to the beta-glucan intervention will receive sufficient IP to cover the entire length of the intervention period (28 days).

Placebo

The placebo product is cellulose, an inert dietary fiber, 500 mg/day (2 capsules per day). The product has a very similar appearance, texture and taste as the beta-glucan product and will have identical packaging. The group randomized to the placebo intervention will receive sufficient IP to cover the entire length of the intervention period (28 days).

Direction of Use

Participants will be instructed to consume the supplement (500 mg/d) for 28 days following the influenza vaccination.

Study design

This is a 6-week randomized, double-blind, placebo-controlled, 2-arm parallel study designed to evaluate the adjuvant effect of beta-glucan dietary supplementation during influenza vaccination. This study will have a 28-day intervention period.

During the pre-screening by telephone or in-person, the study and inclusion and exclusion criteria will be explained. Any restrictions linked to the study will also be explained. Sufficient time will be allowed for the potential participants to decide whether or not they wish to participate in the clinical study. If the potential participant decides to participate, a screening appointment will be scheduled to sign the informed consent and to perform the first study activities.

During the screening appointment (by Zoom or in person), the inclusion and exclusion criteria will be reviewed without responses to the individual items, and if the participant believes they are qualified, the informed consent will be signed via RedCap or in person. Following informed consent, the inclusion and exclusion criteria will be reviewed again, this time with responses to each item and recorded. Each study participant will receive a unique identifier. Within 24-hr prior to Visit 1, links to the Qualtrics demographic form (age, sex, race, and ethnicity) will be sent to participants for completion. Alternatively, the participant will be given the option of completing the questionnaire in person during Visit 1. At Visit 1, a baseline blood draw will be performed, and the participants will be randomized to either the beta-glucan or placebo group and will be instructed about the daily consumption of the IP for 28 days. Participants will then receive an influenza vaccine. Take-away breakfasts will be offered following blood draws. Participants will be requested to complete an online Qualtrics or paper-based daily questionnaire of compliance, and cold, and flu and fatigue symptoms throughout the 28-day study.

A second blood draw within 24-48 hours following their influenza vaccination (Visit 2) will be taken. A final blood draw will be completed on day 28 (Visit 3 - study end). Adverse events, including any illnesses, will be queried.

Randomization

Participants will be randomized to either the beta-glucan or the placebo group in a 1:1 fashion. Randomization will be used in this study to avoid bias in the assignment of participants to intervention, to increase the likelihood that known and unknown participant attributes (e.g., demographics and baseline characteristics) are balanced across intervention groups, and to ensure the validity of statistical comparisons across intervention groups.

Randomization will be done by a computer-generated code, sealed envelope method and completed by an individual not involved in the study. Each random allocation will be arranged to fit on a single sheet of white paper that indicated the study sequence, and which also had blank spaces for the participant's study number, date, the number of IP provided to the participant, and the number of IP returned by the participant. These sheets will be placed in envelopes and sealed. Each envelope will have an envelope number printed on it. The study staff will unseal the envelopes and assign the participant to a study sequence.

Blinding

Prior to delivery to the study site, the beta-glucan and placebo will be coded by an unblinded personnel at Lallemand inc. who will have no direct contact with participants, and no involvement with study procedures. Blinding to intervention will be used to reduce bias during data collection and evaluation of outcomes.

Unblinding

Unblinding should not occur except in the case of an emergency. In the event that a serious adverse event (SAE) occurs, for which the identity of the study supplement administered is necessary to manage the participant's condition, the randomization code for that participant may be broken and the study supplements identified.

All emergency code breaks must be reported to Lallemand inc. project manager within 24 hours. The time, date, reason and who broke the blind, must be documented in the source documents. Details of participants who are unblinded during the study will be included in the final report.

The probiotic and placebo will be double coded, so in the event of an SAE and unblinding of one code, information about 75% of the subjects will remain blinded.

Compliance

Compliance and adverse events will be monitored in the daily questionnaire throughout the intervention phase. Compliance also will be assessed by counting the number of study supplements returned by the participant at the end of the intervention. Compliance is calculated by determining the number of study supplements consumed from start of study IP (V1) to end of study IP (V3) divided by the number expected to have been taken multiplied by 100 to obtain the percentage consumed. Participants found to have a compliance of <80% will be considered noncompliant.

Data Analysis Plan

Statistical consultation will be utilized for data analyses. Statistical methods will be consistent with the CONSORT 2010 Statement (including statistical methods used to compare groups for primary and secondary outcomes and methods for additional analyses, such as subgroup analyses and adjusted analyses).

Data Management Plan

Data about the intervention effects will be collected from the participants electronically and on paper. Data and files will be secured in locked filling cabinets and office space. Paper questionnaires will only include date and research study assigned participant number. Data that is originally captured as hardcopy/paper (e.g., demographics and vital signs) will be transcribed to encrypted electronic files.

Following the completion of the study, identifiers will be removed from data to meet HIPAA deidentification standards (According to the October 2002 Privacy Rule § 164.514.(b).2. the indicated information/will be removed from all study records).

All software applications used in the collection of data will be properly validated following standard computer system validation that is compliant with all regulatory requirements.

Potential Discomforts and Risks

Beta-glucan, a dietary fiber, poses no known risks. Beta-glucan, a fiber, poses no known risks. However, there are some potential discomforts and risks related to the study. Drawing blood from a vein may result in discomfort at the site of puncture; possible bruising and swelling around the puncture site; rarely an infection; and, uncommonly, faintness from the procedure. Some people may feel uncomfortable answering questions about incidence of influenza, cold and flu symptoms, mood and feelings, and fatigue symptoms. Some people may feel uncomfortable or have difficulties swallowing capsules. You can open the capsule and add to a food such as apple sauce if you prefer. There is a risk of possible loss of confidentiality.

Informed consent forms given to all participants specify [name] as the contact in the case of issues or questions arising during the study. In the case that a professional intervention is necessary due to an adverse effect on the study subjects, [name] will contact the appropriate authority or organization pertinent to the circumstance of the event. Serious adverse events will be reported to the sponsor within 24 h of the PI being notified. In the event of a data safety breach, [name] and the appropriate University of Florida personnel will contact participants to inform them of this breach, as well as notify the Institutional Review Board of the University of Florida.

Potential Benefits

It is possible that those participants randomized to the beta-glucan may respond with a greater antibody titer to the influenza vaccine.

Conflict of Interest

The investigator declares no conflict of interest.

Compensation

For participating and completing the study, participants will receive \$25 per blood draw and \$25 per week for daily questionnaire completion for a total of \$175. If a participant drops out during the study, compensation will be prorated at \$25 per week and \$25 per blood draw. Should a participant not complete the entirety of the study due to a withdrawal, disqualification, or any other reason, compensation will be based upon completing pre-determined benchmarks. In all cases, compensation will be provided at the end of the study.

References

- Crooke, Stephen N., Inna G. Ovsyannikova, Gregory A. Poland, and Richard B. Kennedy. 2019. "Immunosenescence and Human Vaccine Immune Responses." *Immunity & Ageing* 16 (1): 25. https://doi.org/10.1186/s12979-019-0164-9.
- Harnack, Ulf, Klaus Eckert, Iduna Fichtner, and Gabriele Pecher. 2009. "Oral Administration of a Soluble 1–3, 1–6 β-Glucan during Prophylactic Survivin Peptide Vaccination Diminishes Growth of a B Cell Lymphoma in Mice." *International Immunopharmacology* 9 (11): 1298–1303.
- Hetland, Geir, and Per Sandven. 2002. "β-1, 3-Glucan Reduces Growth of Mycobacterium Tuberculosis in Macrophage Cultures." *FEMS Immunology & Medical Microbiology* 33 (1): 41–45.
- Lehne, G., B. Haneberg, P. Gaustad, P. W. Johansen, H. Preus, and T. G. Abrahamsen. 2006. "Oral Administration of a New Soluble Branched B-1, 3-D-glucan Is Well Tolerated and Can Lead to Increased Salivary Concentrations of Immunoglobulin A in Healthy Volunteers." *Clinical & Experimental Immunology* 143 (1): 65–69.

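### The note dropping everyone who reports influenza or COVID-19 has no stated scope; as written it leaves no cases in its own outcome and removes ill participants from the fever, symptom and fatigue outcomes

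*Combined protocol and SAP*

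**What the plan says.** The Secondary outcomes list of the combined protocol and SAP includes "Self-reported incidence of influenza and COVID-19" over 28 days. A note inside that bullet reads: "Data of subjects reporting incidence of influenza or COVID-19 during the study will be excluded from the final analysis". The same list contains "Number of subjects with fever during the study", "Number of subjects with cold and flu symptoms" (Modified Jackson Criteria) and fatigue, all over the same 28 days. It also contains an inflammatory cytokine profile sampled at "Pre-vaccine visit, post-vaccine visit (~day 2-3) and study end". The primary outcome is "Influenza-specific antibodies (IgM, IgG influenza A and B").

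Under Study design, "the participants will be randomized to either the beta-glucan or placebo group" at Visit 1, before the vaccine is given. Participants then fill in a "daily questionnaire of compliance, and cold, and flu and fatigue symptoms throughout the 28-day study".

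The Data Analysis Plan refers to statistical consultation and to CONSORT 2010. It names no analysis set, does not use the term final analysis, and does not say which outcomes the note covers.

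**The concern.** The note conflicts with the bullet that contains it: an outcome that counts cases cannot be analysed once every case has been removed.

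If the incidence outcome is tacitly exempt, the rule still applies to everything else. Reporting an illness during follow-up happens after randomization and may be affected by the supplement. Excluding people on that basis means the arms compared are no longer the randomized arms. The people removed are also those most likely to have the events that the fever, symptom and fatigue outcomes are meant to capture.

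Two analysts working from this text could therefore analyse different people for the same outcome. The scope could also be settled after results are seen.

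**Working it through.** **The plan's own figure.** The only figure available is the sample size, 60 + 60 = 120. The Sample Size Calculation section gives no effect size, power or event rate. Every rate below is therefore an assumption, used to show what the rule can do and not what it will do.

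**Three readings of the note**

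| Reading | Incidence | Fever, symptoms, fatigue | Antibodies, cytokines |
|---|---|---|---|
| As written | 0 cases in each arm, whatever the true rates | Reporters removed | Reporters removed |
| Count cases, then exclude elsewhere | Analysable | Reporters removed | Reporters removed |
| Immune outcomes only (stated nowhere) | Analysable | All kept | Reporters removed, still after randomization |

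Under the first two readings, a cytokine sample taken two or three days after vaccination would be dropped because of an illness reported weeks later.

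**How many people.** With illness reported by 2, 5, 10 or 15% of participants, the expected number removed is 120 × rate = 2.4, 6, 12 or 18. Even at 2%, the chance of at least one exclusion is 1 − 0.98^120 = 0.91.

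**Symptoms: the risk difference shrinks.** Assume symptoms in p = 20% of placebo and 12% of beta-glucan participants. Assume also that the same share f of symptomatic people reports illness in both arms, and that nobody else reports. The rate after exclusion is p(1 − f)/(1 − pf), and expected events per arm are 60p(1 − f).

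| f | Placebo vs beta-glucan | Difference (points) | Events analysed | Odds ratio (95% interval) |
|---|---|---|---|---|
| 0 | 20.0 vs 12.0% | 8.0 | 19.2 | 1.83 (0.67–5.0) |
| 0.10 | 18.4 vs 10.9% | 7.4 | 17.3 | 1.83 (0.64–5.2) |
| 0.25 | 15.8 vs 9.3% | 6.5 | 14.4 | 1.83 (0.59–5.7) |
| 0.50 | 11.1 vs 6.4% | 4.7 | 9.6 | 1.83 (0.47–7.2) |

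The odds ratio holds still only because f is equal in both arms and only symptomatic people report. On the risk scale, which suits an outcome defined as a number of subjects, the difference falls by (8.0 − 4.7)/8.0 = 41% at f = 0.50.

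**Fever: the difference disappears.** Assume fever in 80% of reporters and 5% of others in both arms. Fever in all randomized participants is 0.80r + 0.05(1 − r), where r is the reporting rate; among non-reporters it is 5%.

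| r, placebo vs beta-glucan | All randomized | Difference (points) | After exclusion | Removed, 60(r0 + r1) |
|---|---|---|---|---|
| 2 vs 1% | 6.5 vs 5.8% | 0.8 | 5 vs 5% | 1.8 |
| 5 vs 2.5% | 8.8 vs 6.9% | 1.9 | 5 vs 5% | 4.5 |
| 10 vs 5% | 12.5 vs 8.8% | 3.8 | 5 vs 5% | 9.0 |

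No figure is possible for fatigue, because its metric is not stated.

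**Antibodies: the figures do not settle which analysis should be the main one.** Assume responses N(0, 1) and N(0.5, 1), so the true effect is 0.50 SD, and P(report) = expit(b − s × response), so illness is likelier with a low response. By numerical integration, with illness adding 1 SD of titre in the all-randomized column:

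| b | s | Placebo reporting | Reporters excluded | All randomized |
|---|---|---|---|---|
| −4 | 0.5 | 2.0% | 0.498 | 0.496 |
| −4 | 1 | 2.8% | 0.490 | 0.489 |
| −4 | 1.5 | 4.4% | 0.474 | 0.479 |
| −2.5 | 0.5 | 8.3% | 0.492 | 0.483 |
| −2.5 | 1 | 10.5% | 0.469 | 0.464 |
| −2.5 | 1.5 | 13.8% | 0.438 | 0.443 |

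The two estimates differ by 0.001 to 0.009 SD, and neither is always closer to 0.50. If the illness does not raise influenza titre, the all-randomized estimate is 0.50 throughout and only the exclusion is biased. If illness is unrelated to response (s = 0), both give 0.50.

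**The case against.** The strongest reply is that the intent is plain. The primary aim is immune response to the vaccine, an intercurrent infection would confound it, and so the note must concern the immune outcomes only. That reading is reasonable and avoids both main effects. But the document does not state it, and the note sits in the incidence bullet rather than beside the antibody or cytokine outcomes. It would also remain an exclusion made after randomization.

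A reader might go further and infer that the exclusion has no rationale for COVID-19 or for cytokines. The documents do not support that. The cytokine outcome is an inflammatory profile with a study-end sample, and an acute infection of either kind near that sample could plausibly affect it. A reader might also infer that the all-randomized set must be the main antibody analysis; the figures above do not establish this.

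It is also fair to say that the fever example gives zero by construction, since non-reporters have the same rate in both arms. At 60 per arm, the 95% half-widths around its all-randomized differences are about 8.6, 9.6 and 11.0 points, so the trial could not reliably detect differences of 0.8 to 3.8 points in any case. This is a pilot, and the clearest harm is to secondary outcomes. These points limit the weight of the concern. They do not supply the missing scope.

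**Conclusion.** The note is wrong as written and should be corrected; it is no more serious than that. What rests on the text alone is firm: the exclusion is unlimited, it empties the outcome it is attached to, and it removes ill participants after randomization from three related secondary outcomes.

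The size and direction of any bias are not established. A reader might take the tables as a demonstration that the trial's results will be biased, or that only precision is lost. Neither follows. The documents give no illness rates; under assumed ones the exclusion can shrink or remove a risk difference, and it has no effect if nobody reports illness.

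**What to change.** Reword the note in two parts.

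- **Illness outcomes.** Incidence is the number of randomized participants who report influenza or COVID-19, by arm. Fever, cold and flu symptoms and fatigue are analysed in all randomized participants, whether or not an infection was reported.
- **Immune outcomes.** The exclusion applies only to antibodies and cytokines. Each is reported twice: with all randomized participants who have a sample, and without those who reported infection before the sample concerned. The excluded list and the choice of main analysis are fixed before unblinding.

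The cost is one rewritten note and one extra analysis of the immune outcomes, with no added visits, samples or participants. Symptoms and illnesses are already asked about (Study design), and Potential Discomforts and Risks mentions questions on influenza incidence. The date of each infection report must be on record, so that it can be placed before or after each sample. The daily questionnaire as described does not list temperature, but the fever outcome needs it under either wording. The downside is that natural infection may affect the all-randomized immune estimates; the paired analysis lets the reader see how much the result depends on it.

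### Excluding participants who report influenza or COVID-19 removes cases, after randomisation, from the outcomes meant to capture illness

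*Combined protocol and SAP*

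**What the plan says.** The Secondary outcomes list has four outcomes that bear on illness during the 28 days:

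- self-reported incidence of influenza and COVID-19;
- fever, as "Number of subjects with fever during the study";
- cold and flu symptoms, as "Number of subjects with cold and flu symptoms [Time Frame: 28 days] Modified Jackson Criteria";
- fatigue.

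A note in brackets on the incidence outcome states: "Data of subjects reporting incidence of influenza or COVID-19 during the study will be excluded from the final analysis". It refers to the final analysis as a whole. It does not limit the rule to particular outcomes, and it exempts neither the symptom outcomes nor the incidence outcome to which it is attached.

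The Data Analysis Plan names no analysis population and no method for any outcome. It refers to statistical consultation and to CONSORT 2010, so nothing there narrows the note. Under Study design, cold, flu and fatigue symptoms are collected by daily questionnaire for the whole 28 days. Nothing in that section ends data collection for someone who reports an infection.

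**The concern.** Whether a participant reports influenza or COVID-19 is known only after randomisation. It is also closely tied to what the symptom outcomes measure, because a person with influenza is likely to have fever, cold/flu symptoms or fatigue. Dropping such people selects on the outcome.

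If the supplement changes the risk of illness, the arms lose different numbers of people. Those who remain are then no longer the groups that randomisation created. A real reduction in illness would be partly hidden because the arm with more illness would lose more cases. For the incidence outcome the rule defeats the purpose, since everyone who would be counted is removed.

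**Working it through.** **Step 1: what the wording implies for incidence.** A participant counts towards this outcome by reporting influenza or COVID-19. The note removes the data of anyone who does. The remaining count is 0 in each arm, whatever the supplement does. No assumed rate is needed.

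**Step 2: an illustration for a symptom count.** The plan states no figure to reproduce: it gives no event rates, and the sample size of 120 rests on similar published studies. The inputs are:

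- n = 60 per arm (Study Participants);
- assumed proportion with later symptoms, p: 0.20 on placebo and 0.12 on beta-glucan, a true difference of -8.0 points;
- assumed share s of those cases who also report influenza or COVID-19 and are removed: 0.25 or 0.50, the same in both arms.

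Removed cases leave both numerator and denominator:

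- participants removed = n × s × p;
- proportion after exclusion = p(1 − s) / (1 − s·p).

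For s = 0.25:

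- placebo: 60 × 0.25 × 0.20 = 3.0 removed; 0.15 / 0.95 = 0.158;
- beta-glucan: 60 × 0.25 × 0.12 = 1.8 removed; 0.09 / 0.97 = 0.093;
- difference: -6.5 points.

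For s = 0.50:

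- placebo: 60 × 0.50 × 0.20 = 6.0 removed; 0.10 / 0.90 = 0.111;
- beta-glucan: 60 × 0.50 × 0.12 = 3.6 removed; 0.06 / 0.94 = 0.064;
- difference: -4.7 points.

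**Step 3: the size against the noise.** The 95% interval half-width for 0.20 vs 0.12 at 60 per arm is 1.96 × √[(0.20 × 0.80 + 0.12 × 0.88) / 60] = 13.0 points. The shifts of 1.5 and 3.3 points are well inside that. They are nevertheless systematic, and they amount to about 19% (1.5/8.0) and 41% (3.3/8.0) of the assumed effect.

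**Step 4: the case of no effect.** If p and s are equal in the two arms, the formula gives equal proportions and the difference stays at zero. In this illustration the exclusion therefore dilutes a real effect and does not create one.

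The formula applies to counts of participants. Fatigue is listed without a stated measure, so no figure is given for it, but the same participants would be lost.

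**The case against.** The best defence is that the note was probably written with the antibody and cytokine results in mind, where an infection could itself change the measurement. On that reading nobody would apply it to the incidence count, since the result would be empty. This is plausible, but the documents do not say it. The note sits on a clinical outcome, covers the final analysis without limit, and has no analysis plan behind it to restrict it. At the least, the wording must be made explicit.

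It is also fair to say that the illustration rests wholly on assumed rates, that the shifts are small beside the interval width, and that these are secondary outcomes of a study whose sample size section says "This is a pilot study, and thus sample size is based on similar published studies". All of that stands. It limits the consequence but does not justify the rule.

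Two stronger readings are tempting.

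- A reader might infer that the 28-day counts are themselves flawed because they mix early vaccine reactions with later illness. The documents do not support this. The plan never claims to separate the two, and apart from the exclusion the count is a valid randomised comparison of overall symptoms. That the window starts on vaccination day is inferred from the visit schedule, since the fever and cold/flu entries say only 28 days. How many brief reactions would count depends on the Modified Jackson Criteria, which are not reproduced. If assumed reactions of 15% in both arms all counted and were independent of later symptoms, the 28-day rates would be 1 − 0.85 × 0.80 = 0.320 and 1 − 0.85 × 0.88 = 0.252. The -8.0 would then become -6.8, a modest dilution.
- A reader might also infer that excluding infected participants is wrong for the antibody outcome. The note does reach that outcome, but there the infection may disturb the measurement and is not the event being counted. That needs a separate argument, which this point does not make.

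**Conclusion.** The point holds for the incidence, fever, cold/flu and fatigue outcomes, and the note should be changed. As written, it is a post-randomisation exclusion tied to the outcome. For incidence the conclusion follows from the wording alone. For the symptom counts, the illustrated shrinkage from -8.0 to -6.5 or -4.7 points shows direction and order of magnitude only. It depends on the assumed rates of 20% and 12%, on the assumed removed shares of 25% and 50%, and on those shares being equal between arms. If the supplement has no effect on illness or its reporting, this mechanism produces no expected bias.

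The lack of an early/later split of the 28-day window is not an error in the plan.

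**What to change.** Reword the note so that all randomised participants, including those who report influenza or COVID-19, stay in the incidence, fever, cold/flu and fatigue analyses. Present the analysis without them only as a sensitivity analysis, with the number removed in each arm. Make the change before unblinding.

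The cost is a change of analysis wording and a little extra analysis. It uses data that the protocol already plans to collect.

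Optionally, the investigators could add a descriptive early/later breakdown of the daily cold/flu records, with the cut day fixed before unblinding. At 60 per arm and on assumed rates of this order, the intervals within each window would be about ±12 to ±14 points, so it could describe the pattern but not test it.

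### Influenza or COVID-19 during the study removes a participant's data, but the same infection just before Visit 1, or an acute illness that day, is neither screened for nor recorded

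*Combined protocol and SAP*

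**What the plan says.** - **Infection after entry.** A note to the self-reported incidence outcome (Secondary outcomes, 28-day time frame) states: "Data of subjects reporting incidence of influenza or COVID-19 during the study will be excluded from the final analysis".
- **Entry.** Study Participants states: "Subjects who do not meet the inclusion criteria or who meet any of the exclusion criteria will not be eligible to participate". The four items under Exclusion Criteria are "Demonstrate an inability to comply with the study-related procedures"; a past severe reaction or hypersensitivity to the vaccine, its substances or the product; immune-suppressing treatment; and "Be concurrently participating in a clinical trial that, in the judgement of the investigator, would interfere with the evaluation of the study outcomes". The only COVID-19 item among the inclusions is self-disclosed immunisation.
- **History collected.** Additional information collected lists "Vaccinations (including COVID-19 booster) received during the month prior to the study start and during the study period". It asks for no infection history. The form sent before Visit 1 covers age, sex, race and ethnicity (Study design).
- **Visit 1.** Study design gives the order as baseline blood, randomisation and product instructions, then the vaccine. No symptom or temperature check is described before the draw. The daily symptom questionnaire covers the 28 study days.
- **Use of the Visit 1 draw.** It is the reference for the primary outcome (change in influenza-specific IgM and IgG to about day 28) and for the five cytokines.
- **Analysis.** Data Analysis Plan refers to CONSORT 2010. It names no baseline adjustment and no sensitivity analysis.

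**The concern.** By dropping the data of anyone who reports influenza or COVID-19 after entry, the plan treats these infections as making the measurements unusable. It applies no such judgement to the same infections shortly before entry, although they act on the same blood samples.

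A participant recovering from influenza at Visit 1 may have a raised antibody baseline, or antibody still rising for reasons unrelated to the vaccine. Either way, the change to day 28 is not purely a vaccine response. Any acute or recent infection, COVID-19 included, could also alter the inflammatory cytokines at the pre-vaccine draw.

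Because the history is not collected, the analyst could neither identify such participants later nor test whether they matter. The plan does regard other recent exposures as relevant: it records vaccinations in the prior month and bars steroid use in the last 30 days.

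**Working it through.** **Is the gap real?** Each place that could close it:

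| Place | Covers recent infection or illness at Visit 1? |
|---|---|
| Inclusion criteria (5) | No |
| Exclusion Criteria (4) | No |
| Additional information collected | Prior-month vaccinations only |
| Form before Visit 1 | Demographics only |
| Visit 1 sequence | No check stated before the draw |
| Daily questionnaire | The 28 study days only |
| Data Management Plan | Names vital signs as an example of paper data; not linked to eligibility |
| Data Analysis Plan | No rule |

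**Plan's own figure.** The total is 120, 60 per arm. Sample Size Calculation bases it on similar published studies and gives no alpha, power, effect size or SD, so it cannot be reproduced. It serves below only as the denominator.

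**Formula.** Suppose a share f of entrants has a change score displaced by s standard deviations, with the same f expected in both arms. Then:

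- variance inflation V = 1 + f(1 − f)s²
- information lost, in participants = 120(1 − 1/V)

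Neither f nor s is in the documents; all values below are assumptions.

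**Primary outcome.** Only recent influenza is counted, since there is no stated reason for COVID-19 or a cold to move influenza-specific antibody.

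- f = 0.005, s = 1.5: V = 1 + 0.005 × 0.995 × 2.25 = 1.011; lost = 1.3.
- f = 0.01, s = 1.5: V = 1 + 0.01 × 0.99 × 2.25 = 1.022; lost = 2.6.

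The expected number of such entrants is 120f, or 0.6 to 1.2. The chance of at least one is 1 − (1 − f)^120, or 45% to 70%.

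The chance imbalance between arms has standard error s√(2f(1 − f)/60):

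- f = 0.005: 1.5 × √(0.00995/60) = 0.02 SD.
- f = 0.01: 1.5 × √(0.0198/60) = 0.03 SD.

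For scale, with two-sided alpha 0.05 and 80% power (also assumed), 60 per arm detects 0.51 SD.

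**Cytokines.** Any acute or recent infection may count here, so a larger pooled share can be considered. With f from 2% to 10% (2.4 to 12 of 120):

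- f = 0.02, s = 1: V = 1.020; lost = 2.3.
- f = 0.05, s = 1.5: V = 1.107; lost = 11.6.
- f = 0.10, s = 1.5: V = 1.203; lost = 20.2.

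These are upper illustrations. Some of these people would report influenza or COVID-19 on day 1 and be dropped, so they would not add to the analysed variance.

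**The case against.** The strongest reply is that this is a small source of noise in a self-described pilot. Four parts of it deserve an answer.

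- **No bias between arms.** A reader might infer that infected baselines bias the beta-glucan comparison. The documents do not support that: the illness and the baseline draw both precede randomisation, so affected participants are balanced in expectation. This part stands in full.
- **Size.** A reader might carry the loss of up to 20 of 120 over to the primary outcome. That would pool influenza, COVID-19 and any other illness and shift influenza-specific antibody in all of them, for which the documents give no basis. This also stands.
- **Partial cover.** Someone with influenza a few days before Visit 1 may still be ill on day 1, report it and be removed. The phrase during the study has no defined start: Study design calls the study six weeks long, while the outcome time frame is 28 days. A sharp contrast between illness three days before and three days after Visit 1 is therefore too strong. What remains uncovered is illness resolved before Visit 1 and acute illness other than influenza or COVID-19. Removal after day 1 also happens after randomisation, the less safe place for it.
- **Cost of screening.** Visit 1 includes the vaccination, so rebooking delays the vaccine for adults aged 40 or over, some recruited from retirement communities. This is a fair objection to a fixed deferral rule, but not to asking and recording.

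**Conclusion.** The point holds as an avoidable omission with modest consequences. The same infections that remove data during the study are neither screened for nor recorded just before it, and no analysis rule deals with them.

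The consequence is added noise, possible chance imbalance and distorted within-group change. For the primary outcome it is probably small: about 1 to 3 of 120 participants' worth of information, if 0.5% to 1% of entrants had recent influenza and their change moved by 1.5 SD. It may be larger for the cytokines, but how much depends wholly on an assumed share and shift. The documents show that such values can enter, not that they will or how often.

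A reader might also infer that entry screening would cure the removal of data after randomisation. It would not: infections acquired after day 1 would still trigger that rule, and people incubating without symptoms would pass the screen.

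**What to change.** 1. At Visit 1, before the baseline draw and randomisation, ask about influenza or COVID-19 within a recent interval that the sponsor chooses (for example, the prior-month window already used for vaccinations). Record current fever or cold and flu symptoms.
2. Reconcile the entry criteria with the data-exclusion note, so that the infection criterion is applied before randomisation, and define when during the study begins. Leave any deferral of Visit 1 and vaccination to the sponsor and investigator.
3. For those enrolled, compare arms at day 28 with adjustment for the baseline value, and repeat the analysis without participants with recent or current infection as a pre-specified sensitivity analysis. Both are needed: adjustment helps with a raised baseline but not with antibody still rising at the draw.

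The cost is two added questions, a line in the criteria and a short addition to the analysis plan. If the sponsor chooses deferral, a few volunteers would have a later Visit 1 and a later vaccination, and that has to be weighed against the modest gain in precision.
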